## 9.5 Data Analyses

Analysis for Specific Aim 1: Analysis of covariance (ANCOVA) will be used to assess the effects of intervention on changes in measured kyphosis and PTT scores from baseline to the end of the 6 month intervention period, adjusting for the baseline levels of each outcome, as well as for wave of recruitment. Normality and equality of variance of the residuals will be checked.

Analysis for Specific Aim 2: We will also use analysis of covariance (ANCOVA) to assess the effect of intervention on changes from baseline to the end of the 6 month intervention period, in measured HRQoL, as measured by the spinal deformity specific SRS-30 and SF-36 health status instruments, and on secondary measures of physical function including gait speed, spinal extensor muscle strength, Timed Loaded Standing, and the Jug Test. The models will adjust for the baseline level of the outcome.

Analysis for Specific Aim 3: The approach for Aims 1 and 2 will be used to assess intervention effects on muscle strength and density. We will then use structural equation modeling to assess the pathways through which the intervention affects physical function. We hypothesize that changes in kyphosis, strength and density mediate the effect of the intervention on change in physical function. These analyses will also control for mediation by increases in physical activity and aerobic capacity, as well as potential confounders of the changes in kyphosis and strength including age, and baseline kyphosis severity, physical activity level and vertebral fractures. Minimum detectable effects: The sample of 100 will provide 80% power to detect between-group differences of 6.2 points in spinal muscle strength, measured as a percentage of body weight, or 18% of the baseline mean of 35%.

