### **6.2 Description of Evaluations**

**Telephone Screening:** When potential participants call inquiring about study, the research assistant will explain the study and obtain basic demographic information from the caller. Callers will be screened for age, co-morbidities and if they think they have a curvature in their spine.

**Clinic Screening:** After a participant is screened by telephone, they will be invited to attend a group orientation and, an individual screening visit will be scheduled. At this screening visit, [name] and a research assistant will explain the study, obtain informed consent, and screen for additional criteria (kyphosis  $\geq 40$  degrees, active movement in the thoracic spine, gait speed  $\geq 0.6$  meters/second and safety assessments).

**Medical Screening:** Once they meet initial screening criteria a study physician will review their medical criteria and contact their primary care provider before enrolling eligible participants in the study

**Run-in:** Once enrolled in the study and prior to randomization, participants will be expected to attend a group orientation program at the study site where the exercise sessions will take place. Participants will receive an actigraph with verbal and written instructions to wear it at the waist or hip for 1 week to monitor physical activity. The purpose of this run-in period is to allow us to assess whether participants are committed to full participation in the study by documenting attendance and use of the actigraph.

**Test Visit 1 (Baseline and Randomization):** After the run-in period, participants will be randomized to the intervention group or control group. Participants will

be randomized in equal proportions to intervention or control using randomly permuted blocks of randomly selected size 4 stratified by age and gender. Treatment assignments will be generated prior to the study, then placed in order in sealed, opaque envelopes with stratum-specific sequential ID numbers. Consenting participants fulfilling study eligibility criteria will be assigned the next available ID number for the appropriate gender and age stratum. The date and time each envelope is opened will be recorded in a log along with participant ID to ensure integrity of randomization. Participants in this study cannot be blinded, but study staff involved in measuring all outcome measures will not be involved in study visits or the study intervention, and will be blinded to group allocation.

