## **9. STATISTICAL CONSIDERATIONS**

### **9.1 General Design Issues**

**Overview:** The primary analyses will be by treatment assignment, without regard to adherence to the intervention. Improvements in kyphosis, the Modified Physical Performance Test (PPT), and gait speed at 6 months will be co-primary endpoints. The Hochberg procedure will be used in testing the effect of treatment on these three endpoints. However, given fiscal and feasibility limitations on this

single-site study, tests of treatment effects on 5 additional physical function and HRQOL measures (Aim 2), as well as muscle strength and density (Aim 3), and all 9 comparisons at 1 year, will be regarded as secondary and analyzed without penalty for multiple comparisons, but with results clearly presented as hypothesis-generating.

In preliminary analysis, we will use t-, Wilcoxon, chi-square, and Fisher exact tests as appropriate to compare the treatment and control groups in terms of baseline age, gender, co-morbidities, vertebral fractures, physical activity and level of kyphosis. If between-group imbalances are found, sensitivity analyses will be conducted adjusting for the imbalanced covariates. However, the primary analysis will be unadjusted, to avoid inflation of type-I error and erosion of confidence due to model selection.

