### 9.2.1 Treatment Assignment Procedures

**Randomization:** After the run-in period, participants will be randomized to the intervention group or control group. Participants will be randomized in equal proportions to intervention or control using randomly permuted blocks of randomly selected size 4 stratified by age and gender. Treatment assignments will be generated prior to the study, then placed in order in sealed, opaque

envelopes with stratum-specific sequential ID numbers. Consenting participants fulfilling study eligibility criteria will be assigned the next available ID number for the appropriate gender and age stratum. The date and time each envelope is opened will be recorded in a log along with participant ID to ensure integrity of randomization

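### The primary ANCOVA leaves out the age and gender strata used to randomise, and section 9.5 models co-primary gait speed as a secondary outcome without the wave term

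*Combined protocol and SAP*

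**What the plan says.** - **Allocation.** Section 9.2.1 uses "randomly permuted blocks of randomly selected size 4 stratified by age and gender", and section 6.2 has each participant "assigned the next available ID number for the appropriate gender and age stratum". No age cut-point is given anywhere. Wave is not a stratum.
- **Primary model.** Under Aim 1, section 9.5 names kyphosis and PPT (spelled PTT) and describes the ANCOVA as "adjusting for the baseline levels of each outcome, as well as for wave of recruitment". There is no age or gender term.
- **Other covariates.** Section 9.1 says that preliminary tests will "compare the treatment and control groups in terms of baseline age, gender, co-morbidities, vertebral fractures, physical activity and level of kyphosis". If differences appear, "sensitivity analyses will be conducted adjusting for the imbalanced covariates"; but "the primary analysis will be unadjusted, to avoid inflation of type-I error".
- **Gait speed as co-primary.** Section 9.1 says that kyphosis, PPT "and gait speed at 6 months will be co-primary endpoints", tested together by Hochberg. The Précis and sections 1.1, 3 and 9.4.1 also treat gait speed as primary.
- **Gait speed as secondary.** Under Aim 2, section 9.5 lists "secondary measures of physical function including gait speed, spinal extensor muscle strength, Timed Loaded Standing, and the Jug Test". Those models adjust for the baseline value only.

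**The concern.** Stratified allocation balances the arms on age group and gender, which reduces the true sampling variance of the treatment effect when those factors predict outcome. A model without the factors leaves their variance in the residual, so its standard error is too large. The test is then conservative and gives up precision that the design had provided. The fallback in 9.1 does not recover this. It acts only when imbalance is seen, which is what stratification prevents, and then only as a sensitivity analysis.

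For gait speed, section 9.5 is the only place where the treatment-effect models are specified. Read literally, two of the three p-values entering Hochberg come from a model with baseline and wave, and the third from a baseline-only model labelled secondary. That leaves a choice of model open after the data are seen, which could decide a borderline result.

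**Working it through.** **1. The plan's own figure.** Section 9.2 gives 80% power, a Bonferroni-corrected two-sided 5% level, N = 100 with 20% loss (40 per arm), r = 0.8 (gait 0.85), SD 5 for kyphosis and 0.18 for gait speed, and variance reduced by 1 − r². With three co-primaries, alpha = 0.05/3 = 0.0167 and the multiplier is 2.394 + 0.842 = 3.236.

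- Kyphosis: 5 × √(1 − 0.8²) = 3.0, and 3.0 × √(2/40) × 3.236 = 2.17 degrees. This matches the stated 2.2.
- Gait speed: 0.18 × √(1 − 0.85²) = 0.0948, and 0.0948 × √(2/40) × 3.236 = 0.069 m/s.

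The 2.2 is reached only if 5 is the SD before baseline adjustment, although 9.2 calls it residual. Taken literally, 5 × √(2/40) × 3.236 = 3.62 degrees. I use the reading that reproduces 2.2.

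**2. Strata in the model, by formula.** Let R² be the share of post-baseline variance that age group and gender explain. It is an assumption, because the documents give none. The residual SD becomes 3.0 × √(1 − R²), so the kyphosis MDE is 2.17, 2.06 and 1.94 degrees at R² = 0, 0.10 and 0.20.

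**3. Strata in or out, by simulation.** The set-up was 100 participants, four equal age-by-gender strata, permuted blocks of 4, five waves of 20 and 20% random loss, with OLS on arm, baseline and wave, with and without age group and gender. There were 12,000 trials per cell. Monte Carlo error is about 0.2 to 0.3 points on rejection rates and 0.3 to 0.5 on power.

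| R² | Rejection at nominal 5%: planned | with strata | Power at 2.2 degrees, alpha 0.0167: planned | with strata |
|---|---|---|---|---|
| 0 | 4.9% | 5.0% | 76.9% | 76.6% |
| 0.05 | 4.4% | 4.9% | 77.5% | 79.4% |
| 0.10 | 4.1% | 5.0% | 78.0% | 81.7% |
| 0.20 | 3.4% | 5.1% | 79.8% | 86.9% |

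Power sits a little under 80% at R² = 0 because the simulation uses a t reference, spends degrees of freedom on wave and lets loss fall unevenly.

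Sensitivity, planned against strata-adjusted power:

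- 10% loss, as in the Précis: 83.6 vs 83.5, 83.7 vs 85.0, 84.0 vs 87.1 and 85.4 vs 91.4 for the same four R² values.
- An assumed 85/15 gender split: 78.0 vs 81.7 at R² 0.10 and 79.1 vs 86.3 at 0.20.
- SD 5 as literally residual: 30.5 vs 34.8 at R² 0.10.

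**4. Can the 9.1 trigger fire on the strata?** Assume two age groups. Blocks of 4 let the arms differ by at most 2 in a stratum, hence by at most 4 within a gender. With 50 women and 50 men the worst split is 27 v 23 and 23 v 27. Then chi-square = 100 × (27² − 23²)² / 50⁴ = 0.64, p = 0.42. In 10,000 simulated allocations none reached p < 0.05 on gender or age group. The smallest p was 0.42 with equal strata and 0.17 with an 85/15 gender split.

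**5. Gait speed.** Power at 0.069 m/s with the wave term in vs out:

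- wave explains nothing: 76.9 vs 78.5
- wave variance 5% of residual: 76.1 vs 75.6
- wave variance 10% of residual: 76.3 vs 74.4

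**6. State of the Aim 2 sentence.** It names the SF-36 and the Jug Test, which are not outcomes in Table 3 or in 9.4.2. It omits PROMIS, Timed Up and Go and the Six-Minute Walk, which are. It looks carried over from an older outcome set.

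**The case against.** **Nothing promised is lost.** The 2.2-degree MDE rests on baseline adjustment only, and planned-model power does not fall as R² rises. This stands: the loss is relative to a better model and is not a shortfall against the sample-size section.

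**R² may be small.** The background section gives 7 degrees of progression over 15 years in women, or 7/15 × 0.5 = 0.23 degrees in 6 months. If one of two equal age strata progressed at twice that rate and the other not at all, R² = 0.233²/9, about 0.6%. It also gives 6 to 11% higher kyphosis per decade. With a pilot baseline near 55 degrees (6 degrees being 11%), that is 3.3 to 6.0 degrees, of which about 20% (0.65 to 1.2) remains after adjustment at r = 0.8. For strata a decade apart, R² is about 1 to 4%; stacking both extremes gives about 8%. This is a fair reason to expect the lower rows of the table for kyphosis. It says nothing about gender, PPT or gait speed.

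**The imbalance check is wider than the one simulated.** Section 9.1 lists age, allows t- and Wilcoxon tests and sets no threshold. Continuous age could still differ within a stratum. The result in step 4 therefore applies to the strata themselves, and any adjustment would still be only a sensitivity analysis.

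**Class effects.** Treatment is given in small classes, with different therapists by arm. If outcomes cluster by class, adding strata removes some offsetting conservatism. At R² 0.10, rejection at nominal 5% goes from 5.6% to 6.6% at an assumed class ICC of 0.02, and from 8.7% to 10.0% at 0.05. This is a real cost if clustering exists. But the excess comes from ignoring class, and leaving out the strata would be a poor way to offset it.

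**Gait speed is one stale sentence.** Every other section treats it as primary, and the missing wave term may be brevity. Probably so, but no text says which model applies.

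**Conclusion.** Both points hold, as matters of efficiency and clarity. There is no bias, type I error is not inflated by omitting the strata, and the sample size is not wrong on this account.

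For the strata, the change in kyphosis power runs from −0.3 points at R² 0 to +1.9 at 0.05, +3.7 at 0.10 and +7.1 at 0.20. The documents point to the lower part of that range for age and kyphosis. The reason 9.1 gives for limiting adjustment is to avoid data-driven model selection, which does not apply to factors fixed by the randomisation.

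For gait speed, the contradiction moves power by 2 points or less in either direction, but it concerns a co-primary p-value and should be settled before data are seen. In 9.1, the word unadjusted most naturally means not adjusted for covariates found to be imbalanced; this needs only a wording edit.

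The size rests on the assumed R² and wave variance, on SD 5 being the pre-adjustment SD, and on the Bonferroni level. Hochberg is at least as powerful.

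**What to change.** 1. In 9.5, specify one primary ANCOVA for kyphosis, PPT and gait speed: 6-month change on arm, baseline value of that outcome, wave, age group and gender. State the age cut-point used to stratify.
2. Move gait speed to the Aim 1 analysis and reconcile the Aim 2 list with Table 3.
3. In 9.1, say that the primary analysis is not adjusted for covariates beyond baseline outcome, wave and the randomisation strata.
4. Optional: state that the 2.2-degree MDE assumes no within-class correlation, and report a class random-intercept model descriptively. Ten classes less five waves and one arm contrast leave as few as 4 degrees of freedom, so such a model could not rule a class effect out.

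The cost is wording plus 2 to 3 degrees of freedom, with no new data or participants. About 0.3 points of kyphosis power are lost if the strata explain nothing. For gait speed, the full model against the baseline-only model gives 76.6 vs 78.1 if neither wave nor strata matter, 80.5 vs 78.0 at strata R² 0.10 and 85.8 vs 79.7 at 0.20.

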## 9.2 Sample Size and Randomization

**Sample size calculation:** We calculated minimal detectable effects (MDE) with 80% power in 2-sided tests with a Bonferroni-corrected type-I error rate of 5%, in a sample of 100, allowing for within-subject correlation of the baseline and 6-month outcomes, and loss to follow-up of 20% of participants. This trial is powered to detect a difference in change in kyphosis over 6 months of 2.2 degrees (or more) between the intervention and control groups. Although the expected improvement in kyphosis is small, the hypothesis underlying this study is that preventing the expected progression of kyphosis, and improving kyphosis even a small amount, in combination with improvements in strength and conditioning, will result in meaningful improvements in physical function. In addition, the MDE for PPT and gait speed are comparable to clinically meaningful changes defined by Perera. Moreover, the MDE for kyphosis, PPT and gait are plausible in view of our uncontrolled pilot study results showing mean improvement of 6 degrees in kyphosis, 2 points in PPT and 0.05 m/s in gait speed over 3 months. Even if regression to the mean and spontaneous improvement account for almost half of the mean improvement in our pilot study, our 6 month intervention is likely to yield benefits larger than the MDE in our trial. Standard methods for ANCOVA, positing reductions in residual variance by a factor of 1-r due to adjustment for the baseline value of the outcome, were used to obtain these estimates; here r is the within-subject correlation. We used data from the pilot study to estimate r as 0.8 for kyphosis and PPT, and 0.85 for gait speed; we also used pilot data to obtain residual SD (5, 2.6, and .18 respectively).

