#### **9.4 Outcomes**

Baseline characteristics and outcome measures proposed in this study (Table 3) will be collected at baseline and after the 6-month intervention. All outcome measures except computed tomography will be repeated at 1-year after the intervention.

Table 3. Baseline Characteristics and Outcome Measures at Study Visits

Category	Variables: measure	Baseline Testing	6-month Testing	1-year Testing
Demographics - age, gender, ethnicity, education		X		
Aging-related musculoskeletal impairments				
- Bone density: hip BMD (DXA)	X			
- Vertebral fractures: lateral spine radiograph	X			
- Physical activity level: activity counts derived from Actigraph accelerometer	X	X	X	
Kyphosis-related impairments				
- Kyphosis: Cobb angle of kyphosis derived from lateral spine radiographs	X	X	X	
- Kyphosis: Kyphosis derived from Debrunner kyphometer	X	X	X	
- Spinal extensor muscle strength: Biomed computerized dynamometer	X	X	X	
- Spinal muscle density: spinal extensor muscle attenuation from CT scans (HU)	X	X		
Functional performance				
- Composite physical function: Modified Physical Performance Test	X	X	X	
- Gait speed: 4-meter	X	X	X	
- Mobility: Timed Up and Go test	X	X	X	
- Spine endurance: Timed Loaded Standing	X	X	X	
- Aerobic capacity/endurance: Six Minute Walk Test	X	X	X	
Health-Related Quality of Life				
- Spine-specific health-related quality of life: SRS-30	X	X	X	
- General health related quality of life: PROMIS Global Health	X	X	X	
- Physical function related quality of life: PROMIS Physical function short form	X	X	X	

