## **15. SUPPLEMENTS/APPENDICES**

### **I. PROCEDURES SCHEDULE**

Assessment	Phone Screen	Clinic Screen	Medical Screen	Run In	Test Visit 1 (Baseline)	Intervention/Control Visits (1-72)	Test Visit 2 (6 month)	Maintenance Period	Test Visit 3 (1year)
Informed Consent Form		X							
Group Orientation (explain study)		X		X					
Basic Demographics	X				X				
DXA					X				
Lateral Spine Radiograph					X		X		X
Medical History	X		X						
Screen (gait, kyphosis, safety assessment)		X							
Current Medications	X		X						
Contact primary care providers for OK			X						
Inclusion/Exclusion Criteria	X	X	X						
Enroll		X							
Randomize					X				
Intervention/Control Study Visit						X			
Kyphosis: Cobb angle of kyphosis					X		X		X
Kyphosis: Debrunner					X		X		X
Spinal muscle strength: Biodex computerized dynamometer					X		X		X

Assessment	Phone Screen	Clinic Screen	Medical Screen	Run In	Test Visit 1 (Baseline)	Intervention/Control Visits (1-72)	Test Visit 2 (6 month)	Maintenance Period	Test Visit 3 (1year)
Spinal muscle density: CT scans					X		X		
Functional Performance					X		X		X
Health-Related Quality of Life					X		X		X

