Are you currently under a physician's care for this?

- Yes
- No

Prior spine surgery

- Yes
- No
- Don't know

what type?

- spinal fusion
- laminectomy
- foramenotomy
- other

Year of diagnosis:

---

Are you currently under a physician's care for this?

- Yes
- No

Scoliosis

- Yes
- No

Year of diagnosis

---

Are you currently under a physician's care for this?

- Yes
- No

Cerebellar problems (ataxia)

- Yes
- No
- Don't know

Year of diagnosis:

---

Are you currently under a physician's care for this?

- Yes
- No

Chemical dependency (alcohol or drugs)

- Yes
- No
- Don't know

Year of diagnosis:

---

Are you currently under a physician's care for this?

- Yes
- No

Depression

- Yes
- No
- Don't know

Year of diagnosis:

---

Are you currently under a physician's care for this?

- Yes
- No

Post traumatic stress disorder (PTSD)

- Yes
- No
- Don't know

Year of diagnosis:

---

Are you currently under a physician's care for this?

- Yes
- No

Latex allergy

- Yes
- No
- Don't know

Year of diagnosis:

---

Are you currently under a physician's care for this?

- Yes
- No

Was time to walk over 4 m course collected?

- Yes
- No

Time to walk over a 4 meter course:

---

(seconds)

why not?

- Participant refused
- Participant unable

Was usual Kyphosis measured?

- Yes
- No

record :

---

(degrees)

why not?

- Participant refused
- Participant unable

was Best kyphosis measured?

- Yes
- No

record:

---

why not?

- Participant refused
- Participant unable

Difference between Best and usual kyphosis:

---

Sit to stand from 16" high chair (Able to perform with arms crossed over chest)

- Yes
- No

Safety tests:

Able to transition from standing to recumbent on the floor and rise from the floor to standing

- Yes
- No

Able to lift both arms to shoulder level

- Yes
- No

Able to stand with feet side by side for 30 seconds

- Yes
- No

Able to stand with feet hip-width apart for 60 seconds.

- Yes
- No

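### The co-primary gait-speed ANCOVA leaves out a pre-randomisation 4-metre walk already recorded at screening; prespecifying it would be a nearly free gain in precision, of uncertain size

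*Combined protocol and SAP*

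**What the plan says.** Section 9.1 names three co-primary endpoints: kyphosis, the modified PPT and "gait speed at 6 months will be co-primary endpoints". Section 9.5 does not carry this through. Its Aim 1 paragraph specifies ANCOVA for kyphosis and PPT only, "adjusting for the baseline levels of each outcome, as well as for wave of recruitment". Gait speed appears in the Aim 2 paragraph among the secondary function measures. Those models adjust for the baseline level of the outcome, and wave is not mentioned. Section 9.2 also assumes a single baseline value when it sizes the trial.

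A second pre-randomisation walk exists. In Appendix I the row beginning "Screen (gait, kyphosis, safety assessment" is ticked at the clinic screen. The matching form items, printed at the end of the Medical History form beside the safety tests, record "Time to walk over a 4 meter course" in seconds. The 4-metre walk is repeated at Test Visit 1 (Table 3 and the physical performance form). Section 9.2.1 places randomisation after the run-in, so the screening walk comes first. No section uses it as a covariate.

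**The concern.** Section 9.2 draws much of its power from baseline adjustment. One 4-metre walk is a noisy covariate: section 9.4.1 gives a test-retest reliability of 0.90 and an ICC of 0.79 for walks two weeks apart. Two walks can remove more residual variance than one, and a prespecified covariate measured before randomisation does not bias the comparison.

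Gait speed is also where the margin is thinnest. Section 9.2 calls its detectable differences plausible in view of the pilot, where gait speed improved by 0.05 m/s. The plan's own method gives a detectable difference of 0.069 m/s for gait speed, which is larger than that gain. At stake is the width of one co-primary confidence interval, and a data item that participants have already supplied.

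**Working it through.** **Inputs from section 9.2.** The detectable differences are computed for "80% power in 2-sided tests with a Bonferroni-corrected type-I error rate of 5%, in a sample of 100", with "loss to follow-up of 20% of participants". That leaves 80 completers, or 40 per arm, because participants are "randomized in equal proportions to intervention or control". With three co-primaries, alpha is 0.05/3. The SDs are 5 degrees (kyphosis) and 0.18 m/s (gait speed); the baseline-to-6-month correlations are 0.80 and 0.85.

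**Formula.** MDE = (2.394 + 0.842) × SD × √(1 − R²) × √(2/40), where R² = r² with one baseline value.

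**Reproducing the plan's figure.** Kyphosis: 3.236 × 5 × √(1 − 0.64) × 0.2236 = 2.17 degrees, against the stated 2.2. The SDs are called residual, but 2.2 reproduces only when √(1 − r²) is applied to them; without it the result is 3.62.

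**Gait speed, one baseline.** 3.236 × 0.18 × √(1 − 0.7225) × 0.2236 = 0.0686 m/s. Power for a difference of 0.05 m/s is 48.6%.

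**Gait speed, two walks.** R² = (r1² + r2² − 2·r1·r2·ρ)/(1 − ρ²). Here r1 = 0.85 is the correlation of the baseline walk with outcome, r2 that of the screening walk with outcome, and ρ the correlation between the two walks. The documents give neither r2 nor ρ for this trial, so both are assumptions. With r2 = 0.85 and ρ = 0.90:

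- R² = (0.7225 + 0.7225 − 1.3005)/0.19 = 0.7605
- residual variance 0.2395 against 0.2775, a cut of 14%
- equivalent completers 0.2775/0.2395 = 1.16

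| r2 | ρ | Cut in residual variance | MDE (m/s) | Power at 0.05 m/s |
|---|---|---|---|---|
| single baseline | – | – | 0.0686 | 48.6% |
| 0.85 | 0.90 | 14% | 0.0637 | 55.7% |
| 0.85 | 0.95 | 7% | 0.0663 | 51.9% |
| 0.80 | 0.90 | 2% | 0.0678 | 49.7% |
| 0.765 (= 0.85 × 0.90) | 0.90 | 0% | 0.0686 | 48.6% |

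In the last row the screening walk relates to outcome only through the baseline walk, so it adds nothing.

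**Do the inputs fit together?** A 6-month correlation of 0.85 sits above the two-week ICC of 0.79. If ρ = 0.79 and r1 = r2 = 0.70 to 0.79, the standard error falls by 6% to 10%, but from a worse start (single-baseline MDE 0.093 to 0.080 m/s). Combining r1 = r2 = 0.85 with ρ = 0.79 gives a 17% lower standard error. That mixes figures that do not belong together, so it is an upper bound and not an estimate.

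**The case against.** The strongest reply is that nothing is broken. Sections 9.2 and 9.5 agree on single-baseline adjustment, the ANCOVA is valid, and 2.2 degrees reproduces. That stands: this is an efficiency proposal.

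The second reply is that the gain rests on the screening walk predicting outcome as well as the baseline walk. It may not. It is taken earlier, and it serves as an entry gate at 0.6 m/s (section 4.1), which may weaken its correlation with outcome. That stands too, and it is why the range runs down to zero.

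Third, the pace is unsettled. Section 9.4.1 describes usual and fast walking, while the screening and testing forms each record one unlabelled time. The extra covariate is a true repeat only if the paces match.

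The statement in section 9.1 that the primary analysis is unadjusted is not a bar. In context it concerns covariates picked after an imbalance is seen, and baseline adjustment is already planned.

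A reader might infer that all three co-primary models waste a second baseline. The documents do not support this. PPT is first measured at Test Visit 1. The kyphosis outcome is the radiographic Cobb angle, with no film before that visit. Table 3 lists "Kyphosis: Kyphosis derived from Debrunner kyphometer" as a separate measure, by a different instrument. Section 2.1 calls the two strongly correlated but gives no figure. If Debrunner relates to the later Cobb angle only through the baseline Cobb angle (for example 0.64 = 0.80 × 0.80), the gain is zero. The pilot kyphosis results in section 2 are also Debrunner readings, so the 0.8 in section 9.2 may not be a Cobb-to-Cobb correlation.

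**Conclusion.** The point holds for gait speed alone, as a near-costless improvement. At a screening-to-baseline correlation of 0.90, the cut in residual variance is 14% if the two walks predict equally well (MDE 0.069 to 0.064 m/s, about 16% more completers), about 2% if the screening walk correlates 0.80 with outcome, and nothing if it adds no information beyond baseline. Both correlations are assumed; SD, r, alpha and loss to follow-up come from section 9.2. Even at 14%, the detectable difference stays above the pilot gain of 0.05 m/s, so the change helps but does not make gait speed well powered for that gain.

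The placement of gait speed in section 9.5 is a plain inconsistency with section 9.1 and needs correcting whether or not the second walk is used. Baseline Debrunner in the Cobb model is at most optional, with a gain that may be near zero. PPT is unaffected.

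**What to change.** In section 9.5, move gait speed from the Aim 2 to the Aim 1 paragraph and state which walking pace is the outcome. Prespecify ANCOVA of 6-month change on treatment, adjusting for baseline 4-metre speed, screening 4-metre speed and wave. Include the screening walk if it was taken at the outcome's pace; confirm this from the screening procedure before any unblinded analysis and label the pace on both forms. Keep the single-baseline model as a sensitivity analysis.

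The cost is wording. The screening walk uses one degree of freedom. Wave, which gait speed takes on with the Aim 1 model, uses four (five waves less one). With 80 completers that leaves 80 − 8 = 72 residual degrees of freedom (intercept, treatment, two walks, four wave terms). No new visit, test or participant is needed. Because entry depends on the screening gait speed, that value should be nearly complete among those randomised.
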